5.4.5. Immunological and molecular assays

Regarding immunological assays, inflammatory and specific response will be assessed in PBMC and in plasma at Visits 2, 6, and 8.

General immune phenotype of cellular populations, including activation markers: PBMCs from visits 2, 6 and 8 will be analyzed by flow cytometry, using an 11-colours panels, including: CD3, CD8, CD4, CD45RA, CCR7, CD27, CD28, CD38, HLA-DR, PD-1, viability. In addition to activation and PD-1 longitudinal assessment, change in the percentage of naïve, memory and activated CD4+ and CD8+ T cell subsets changes in peripheral blood and in GALT (rectal tissue), will be analyzed in different time points in comparison to baseline (before treatment with ABX464).

Inflammatory response will be quantified using ELISA assay. This assay is based on the detection of cytokine production in the plasma.

5.4.6. Rectal Biopsy/ Flexible sigmoidoscopy

Flexible sigmoidoscopy is routinely utilized in gastrointestinal and HIV research clinical trials. Based on data from more than 1,000 procedures. Flexible sigmoidoscopy with up to 20 biopsies taken using jumbo forceps has shown a low adverse event rate, even when performed repeatedly in clinical trial participants.

At baseline (Day 1), at Day 28, at Day 56 (only for cohort 1&3) and at Day 84/Day 112 (only for cohort 3) a flexible sigmoidoscope will be inserted into the rectum of the subjects to 15 cm from the anal margin, where 15 to 20 biopsies will be collected for flow cytometry, ex vivo tissue infectivity assays, and PK.

5.4.7. Microbiome assays

The microbiome composition might affect the reservoir size and is key to mucosal immunity. Microbiome specimen will be collected using a rectal swab before each flexible sigmoidoscopy procedure.

The microbiota will be characterized using 16S rDNA Illumina (R) deep sequencing and analyzed using similar methods [5]. Briefly, to characterize alpha diversity in each dataset, species richness (Observed richness and the numeric richness estimators Chao1 and ACE) as well as diversity / evenness measurements (Shannon and Simpson indices) we will use Vegan [6] and Biodiversity-R R packages, respectively. Study ordination analyses will be performed using non-metric multidimensional scaling (NMDS) in a two-dimensional space based on ecological distance matrices calculated by Bray-Curtis dissimilarities as implemented in R/phyloseq wrappers. Findings will be further confirmed using different ecological distances implemented in the same package. The influence of different covariates (demographical, medical, biological) on microbiome structure similarity measures will be tested using permutational analysis of variance using Bray-Curtis distances as implemented in adonis function from R/Vegan package. To further explore structuring of our datasets in clusters, we will use the Partitioning Around Medoids (PAM) algorithm [7] as implemented in the R/cluster[8] package. Silhouette coefficients will be used to assess the goodness-

of-fit of the different possible partitions of each dataset. To assess genus abundance, OTU counts will be collapsed to the bacterial genus level and genus proportions will be calculated for each sample. The differential genus abundance by categories will be compared using the Kruskal-Wallis and Dunn's post-hoc test when required. Multiple comparisons will be corrected with the Benjamini-Hochberg method [9] The LEfSe algorithm [10] will be used to describe genus significantly enriched in different categories.

5.4.8. Pharmacokinetics

Plasma and tissue ABX464 and its metabolite concentrations will be determined by liquid chromatography tandem mass spectrometry (LC-MS/MS) methods validated for all matrices by ATLANBIO.

ABX464

After single oral administration of 50 to 200 mg ABX464, ABX464 is relatively quickly absorbed and undergoes a very extensive biotransformation into its N-glucuronide metabolite, NGlc.

In most of the subjects, regardless of the dose, ABX464 plasma concentration is generally not measured after 8 to 10 h post-dose. Cmax is generally observed within the first 2 h post-dose and then ABX464 plasma concentrations decreased with a $t_{1/2}$ of about 1 to 2 h.

ABX464-N-glucuronide's plasma concentrations were markedly higher than those of the parent drug with mean Cmax about 200 to 300-fold higher than ABX464 Cmax. Cmax was observed around 4 h post-dose with a very limited variability thereafter ABX464 NGlc was slowly eliminated and had a $t_{1/2}$ of 90 to 110 h.

Relationship between rate and extent of absorption of ABX464 and ABX464 dose is quite erratic with a reduced increase with the dose up to 150 mg and saturation like behavior at 200 mg.

ABX464-N-glucuronide's exposure-dose relationship is somehow comparable to that of ABX464 although increase of C_{max} and AUCs tend to be dose proportional between 50 and 150 mg.

Since ABX464 undergoes a high level of biotransformation, ratios between metabolite and parent drug appear to be unchanged across the studied dose range but inter-individual variability prevented from definite conclusions.

Therefore, ABX464 should rather be considered as a pro-drug with regard to its short $t_{1/2}$. Its metabolite, ABX464-N-glucuronide exhibits markedly higher blood concentrations and has a much longer $t_{1/2}$ which could be of pharmacological interest. Last, dose-exposure relationship appears erratic between 50 and 200 mg but tends to linearity up to 150 mg.

ABX464 was shown to have a very short $t_{1/2}$ (1 to 2 h), so steady-state is virtually reached at the second administration, while ABX464-N-glucuronide has a $t_{1/2}$ of 90 to 110 h, meaning that steady-state is reached after 19 to 22 days of administration. Intense PK blood collection is planned to be done on Day 1 (initiation of ABX464 administration) and Day 28 (final dose of ABX464) to characterize accumulation and decay of ABX464 and its metabolite (ABX464-N-glucuronide) in plasma and PBMC.

Additional blood PK samples will be collected on Days 35 and 56 to characterize the terminal decay of ABX464. In addition, ABX464 and ABX464-N-glucuronide will be quantified in rectal tissue biopsies collected during Visit 2, 6 and 8.

A total of 18 blood samples per HIV negative subjects and 18 blood samples per HIV positive subjects will be collected for PK assessment. These samples will be processed according to the appendix 3 in order to get Plasma and PBMC samples.

Blood samples for determination of ABX464 and ABX464-N-glucuronide, will be collected from all subjects using direct venipuncture or an indwelling catheter.

Then, the following PK parameters will be derived for ABX464 and ABX464-N-glucuronide

- C_{max}, t_{max}: the maximum plasma concentration (Cmax) and the time taken to reach Cmax (tmax) will be obtained directly from the concentration-time data.
- AUC_{0-τ}: the area under the concentration-time curve from time zero to the time of dosing interval τ (24 h post-dose for ABX464 and ABX464-N-glucuronide). If no concentration can be measured at this time point, AUC_{0-last} (from time zero to the last quantifiable concentration) will be calculated. Both parameters will be presented independently. For both parameters, a linear trapezoidal method will be used.

Moreover, evaluation of steady-state will be made by visual inspection of the pre-dose concentration measurement collected over the study duration.

In addition, five rectal biopsies at each time point will be sent to ALTANBIO for tissue PK determination.

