3. INVESTIGATIONAL PLAN

3.1. Study design

3.1.1. Design and methodology

The ABX464-005 study is a Phase Ib, sequential cohort open label trial designed to provide additional safety and compartmental PK data on ABX464.

The study will also generate exploratory immunological and virological data that combined with the compartmental PK data will help further characterize the mechanism of action of ABX464.

The study will enroll both HIV-infected (N=24) and HIV-uninfected (N=12) study subjects in three distinct cohorts:

- Cohort 1: 12 HIV-infected subjects treated with ABX464 150 mg o.d. for 28 days
- Cohort 2: 12 HIV-uninfected subjects treated with ABX464 50 mg o.d. for 28 days
- Cohort 3: 12 HIV-infected subjects treated with ABX464 50 mg o.d. for 84 days

HIV-infected subjects will add the investigational product to their current antiretroviral regimen whereas the HIV-uninfected subjects will only receive the investigational product.

Cohort 1 will consist of 12 HIV infected subjects. After full enrollment and an interim analysis (including PK and immunological markers) of Cohort 1, Cohort 2 and 3 will begin enrollment and will consist of both HIV infected (n=12) and HIV uninfected (n=12) subjects.

Subjects who successfully complete a screening visit (Visit 1) will advance to a Baseline visit (Visit 2; Day 1). During this visit all subjects will undergo a physical examination and have blood and rectal tissue samples collected.

The rectal tissue samples will be collected before initiating oral dosing with the investigational product (150 mg or 50 mg of ABX464).

After receiving the first dose of ABX464, additional blood PK samples will be collected at 0h, 0.5h, 1h, 1.5h, 2h, 4h, 6h and 8 hours.

All subjects will receive the investigational product once daily for 28 days (Cohorts 1 &2) and for 84 days (Cohort 3).

At Day 28 for subjects enrolled in cohort 3 and at the end of the treatment period (End of Rx Visit; Day 28 for Cohorts 1&2 and Day 84 for Cohort 3) subjects will undergo a physical examination and have blood and rectal tissue collected. PK blood samples will be collected at 0h, 0.5h, 1h, 1.5h, 2h, 4h, 6h and 8 hours.

HIV infected subjects will continue with their antiretroviral regimen i.e. there will be no antiretroviral treatment interruption in this study.

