- Viral Load, CD4/CD8 count (HIV infected Subjects);
- Perform PK blood sample (at 9AM \pm 1hour);
- Adverse event assessment.

5.3.8. End of Study Visit (D56 for cohort 1&2 or D112 for cohort 3; \pm 7 days)

- Physical examination and vital signs;
- Microbiome specimen collection (swabs);
- Hematology (incl. INR and PT if clinically indicated);
- Biochemistry;
- Urine GC/CT NAAT & Rectal GC/CT NAAT;
- HIV serology (HIV uninfected participants)
- 12 lead ECG;
- Viral Load, CD4/CD8 count (HIV infected Subjects);
- Blood collection for HIV reservoir assessment (HIV infected Subjects) and immuno-evaluation;
- Flexible sigmoidoscopy with collection of rectal biopsies (Cohort 1 and 3 only)
- Perform PK blood sample (at 9AM \pm 1hour);
- Adverse event assessment.

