- Mean plots showing the data of both treatments (administration alone and co-administration with ABX464);
- By subject plots with the treatments on separate plots (spaghetti plots).

Formal PK Statistics

Evaluation of drug-drug interaction

The relative bioavailability (F_{rel}) after multiple dose administration with either co-administration of ABX464 will be evaluated on PK parameters determined on Day 28.

The comparison will be performed on C_{max} and $AUC_{0-\tau}$ using a 1-way ANOVA model with treatment as main effect on logarithmically transformed data. For each parameter, a point estimate for the ratio of geometric means (ARTs with 150 mg doses of ABX464) will be obtained by calculating the difference of least square means on the logarithmic scale and subsequent back transformation with the exponential function. Likewise, 90% confidence interval for the ratios will be obtained by back transforming the 90% confidence intervals of least square mean differences on log-transformed PK parameters.

Moreover, evaluation of steady-state will be made by visual inspection of the pre-dose concentration measurement collected over the study duration.

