#### 4.3 Pharmacokinetic Endpoint

ABX464 has a very short  $t_{1/2}$  (1 to 2 h) and generally no drug could be quantified after 10h post-dose, so steady-state is virtually reached at the second administration.

NGlcABX464 (main ABX464 metabolite) has a  $t_{1/2}$  of 90 to 110 h, meaning that steady-state is reached after 19 to 22 days of administration.

Pharmacokinetic parameters are assessed in plasma, in PBMC and in rectal mucosa.

Intensive Pharmacokinetic runs are conducted after the first dose of ABX464 (Day 1) and for

② Cohort 1: at Day 28 and at Day 56 for plasma, PBMC and rectal tissue.

② Cohort 2: at Day 28 and at Day 56 for plasma and PBMC. Rectal tissue only at Day 28.

② Cohort 3: at Day 28, Day 84 and Day 112 for plasma, PBMC and rectal tissue.

Following PK parameters will be derived for ABX464 and ABX464-N-glucuronide

- $C_{max}$ ,  $t_{max}$ : the maximum plasma concentration ( $C_{max}$ ) and the time taken to reach  $C_{max}$  ( $t_{max}$ ) will be obtained directly from the concentration-time data.
- $AUC_{0-\tau}$ : the area under the concentration-time curve from time zero to the time of dosing interval  $\tau$  (24 h post-dose for ABX464 and ABX464-N-glucuronide). If no concentration can be measured at this time point,  $AUC_{0-last}$  (from time zero to the last quantifiable concentration)

will be calculated. Both parameters will be presented independently. For both parameters, a linear trapezoidal method will be used.

In addition, five rectal biopsies at each time point will be sent to ALTANBIO for tissue PK determination.

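### AUC0-τ is defined over 24 h but every profile ends at 8 h, so it cannot be computed; for the plasma metabolite the fallback covers only about one third of the dosing interval

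*Protocol*

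**What the plan says.** The primary endpoint (Protocol 5.2, SAP 4.1) is Cmax and AUC, with the type of AUC not named. Protocol 5.4.8 then derives AUC0-τ, defined as "the area under the concentration-time curve from time zero to the time of dosing interval τ (24 h post-dose for ABX464 and ABX464-N-glucuronide"). Protocol 9.2.1 and SAP 4.3 give the same definition.

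The fallback is AUC0-last, taken to the last quantifiable concentration. It is triggered by the condition "If no concentration can be measured at this time point". Both AUCs are to be shown separately, each by the linear trapezoidal rule.

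On Day 1, "additional blood PK samples will be collected at 0h, 0.5h, 1h, 1.5h, 2h, 4h, 6h and 8 hours" (Protocol 3.1.1). The Day 28 and Day 84 profiles use the same times: "PK blood samples will be collected at 0h, 0.5h, 1h, 1.5h, 2h, 4h, 6h and 8 hours". The synopsis sampling table applies them to plasma and PBMC alike. The only later PK draws are single ones, one week and four weeks after dosing stops (Protocol 5.3.7 and 5.3.8: "Perform PK blood sample (at 9AM" within an hour either way). Protocol 5.4.8 gives the total: "A total of 18 blood samples per HIV negative subjects and 18 blood samples per HIV positive subjects will be collected for PK assessment".

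The intensive sampling on Day 1 and Day 28 is intended "to characterize accumulation and decay of ABX464 and its metabolite (ABX464-N-glucuronide) in plasma and PBMC". SAP 11.3.1 summarises the primary endpoint descriptively, and SAP 10.2 rules out imputation of missing data.

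**The concern.** An AUC to 24 h by the trapezoidal rule needs a concentration at or near 24 h. No such sample is scheduled, and neither document describes an extrapolation or a substitute value. The AUC0-τ table would therefore be empty, and a rule meant for the occasional unmeasurable sample would decide every AUC in the study.

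This matters because AUC is one of the two primary parameters and the primary objective names the metabolite. Protocol 5.4.8 treats the parent as closer to a pro-drug and points to the metabolite's higher concentrations and longer half-life as of possible pharmacological interest. The metabolite is also the analyte that an 8 h window captures least well.

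**Working it through.** **Is a 24 h sample hidden somewhere in the schedule?** No.

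- Sample count: 8 (Day 1) + 8 (Day 28) + 1 + 1 = 18, the stated total. This fits Cohorts 1 and 2 only. Cohort 3 has three profiles, so 3 × 8 + 2 = 26, and the total of 18 is no evidence about Day 84.
- Blood volume (Protocol Table 5, 12 mL per PK time point), HIV-positive Day 1: 8 × 12 + 5 + 3 + 10 + 3 + 50 = 167 mL, as stated. A ninth draw would give 179 mL. The Cohort 3 Day 28 and Day 84 volumes are also 167 mL.
- HIV-negative Day 1: 96 + 5 + 3 + 20 = 124 mL, as stated. A ninth draw would give 136 mL.

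**Metabolite in plasma.** Inputs from Protocol 5.4.8: tmax about 4 h, half-life 90 to 110 h. Five half-lives are 18.75 to 22.9 days, in line with the stated 19 to 22 days to steady state. The curve shape is my assumption:

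C(t) = ka/(ka − k) × [exp(−kt) − exp(−ka·t)], with k = ln 2 / half-life and ka solved so that tmax = 4 h (1.29 to 1.35 per h), doses superposed every 24 h.

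| Half-life | AUC0-8/AUC0-24, Day 1 | Day 28 | Day 28/Day 1 ratio on AUC0-24 | Same ratio on AUC0-8 |
|---|---|---|---|---|
| 90 h | 0.330 | 0.350 | 6.07 | 6.48 |
| 100 h | 0.329 | 0.349 | 6.66 | 7.10 |
| 110 h | 0.328 | 0.347 | 7.23 | 7.71 |

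The first two result columns are exact integrals. The AUC0-8 ratio uses the linear trapezoid on the planned times. Day 84 shares match Day 28. A flat curve gives 8/24 = 0.333, and a linear rise to 4 h gives 0.286 to 0.289 on Day 1, so one third depends little on the model. The AUC0-8 accumulation ratio runs about 7% above the 24 h ratio (7.10/6.66 = 1.066), and about 19% above it with the linear rise.

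**Can the Day 28 and Day 84 pre-dose sample stand in for 24 h?** I take the 0 h sample as pre-dose.

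- The fraction of steady state before the Day 28 dose, after 27 × 24 = 648 h, is 1 − 2^(−648/half-life): 0.993 at 90 h and 0.983 at 110 h.
- Adding a 24 h point equal to the 0 h value, the linear trapezoid gives 99.9 to 100.0% of the true AUC0-24 on both days.

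**Parent.** Protocol 5.4.8 gives a half-life of 1 to 2 h, Cmax within 2 h, and concentrations generally not measured after 8 to 10 h.

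- With tmax 1 to 2 h, the 0-8 h window holds 0.88 (half-life 2 h, tmax 2 h) to 0.99 (half-life 1 h) of AUC0-24. I used a linear rise where no one-compartment curve fits.
- If a subject's last quantifiable sample is at 4 h, the one-compartment share falls to 0.55 to 0.88, so AUC0-last can cover different spans in different subjects.
- Setting the 24 h value equal to the 0 h value would be wrong here. The straight line from 8 h to a near-zero value at 24 h overstates AUC0-24 by about 1 to 20% (tmax 0.5 to 2 h): 13% at half-life 2 h and tmax 1 h, 20% at tmax 2 h. Plain AUC0-8 is then about 7% and 13% low.

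**The case against.** The strongest reply is that the plan already covers this. AUC0-last is defined, will be reported under its own name, and is computable. The primary endpoint says only AUC, the analysis is descriptive, and no sample-size calculation depends on it. This stands in part and rules out four stronger readings.

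- A reader might infer that a partial AUC is silently passed off as a daily AUC. The documents do not do that. What they omit is that the fallback will apply every time.
- A reader might infer that the study obtains no primary AUC at all. Only AUC0-τ is lost, and for the parent the loss is modest.
- A reader might cite the formal Day 28 comparison in Protocol 9.2.1 ("The comparison will be performed on C_{max} and" AUC0-τ) as an analysis left without data because of this gap. It is poor evidence. That comparison is described as a drug-interaction analysis of antiretrovirals with ABX464, no antiretroviral sampling or ABX464-free reference period is scheduled, and SAP 11.3.1 keeps only descriptive summaries. A 24 h sample would not rescue it.
- A reader might carry the one-third figure over to PBMC. The documents give no PBMC half-life or tmax, so only the 8 h cut-off is established there.

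An accumulation ratio is also not among the parameters listed in 5.4.8 or 9.2.1, so the bias in that ratio matters only if one is reported.

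The reply does not remove the core fact: a parameter defined to 24 h is scheduled with samples to 8 h, and for the metabolite the substitute leaves out about two thirds of the interval.

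**Conclusion.** The mismatch is real and follows directly from the documents: AUC0-τ cannot be computed for either analyte on any profile day, and AUC0-last always takes its place. For the metabolite in plasma, AUC0-last is in effect AUC0-8, about one third of AUC0-24, and would be about three times too low if read as daily exposure. For the parent, the 8 h window is nearly complete. The remaining weakness there is that AUC0-last can end at a different time in each subject.

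The 8 h cut-off needs no model. The fractions rest on the protocol's half-life and tmax and on assumed curve shapes, and apply to plasma only.

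**What to change.** Amend Protocol 5.4.8 and 9.2.1 and SAP 4.3 and 11.3.1 as follows.

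- **(a) Metabolite, Day 28 and Day 84.** Compute AUC0-24 with that day's pre-dose concentration as the 24 h value. State this as a steady-state assumption (98 to 99% of steady state at Day 28 in plasma) and as an explicit exception to SAP 10.2. For PBMC, flag the assumption as unverified.
- **(b) Day 1.** Drop AUC0-τ and report AUC0-8, labelled as such.
- **(c) Parent.** Report AUC over a fixed 0-8 h window on all profile days, and do not use the pre-dose value as the 24 h value. Give one rule for values below the limit of quantification before 8 h. At present Protocol 9.2.1 sets them to zero before the first quantifiable sample and to missing after it, while SAP 10.1 uses half the limit.
- **(d) Accumulation ratio, if reported.** Use AUC0-8 on both days. Note that for the metabolite it runs about 7% above the 24 h ratio in the one-compartment model, and more for other curve shapes.

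The cost is wording only, with no new samples. The downside is that the metabolite's AUC0-24 on Day 28 and Day 84 rests on the steady-state assumption. A real 24 h draw would remove it, at one further 12 mL sample per profile: 20 PK samples per subject in Cohorts 1 and 2, and 179 mL instead of 167 mL on Day 1 in HIV-positive subjects.

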5.4.9. Transcriptomics / Proteomics

Two rectal biopsies will be cryopreserved at -80°C, one in RNA later and another one snap-frozen, to enable future transcriptomics and proteomics analyses. The decision of performing such proteomics and/or transcriptomics analyses will depend on the results obtained from the remaining study analyses.

5.5. Summary of blood samples

Table 5 below summarizes the volume of blood to be sampled at each study visit.

Table 5: Summary of Blood Volumes (mL)

	HIV positive (Cohort 1)	HIV positive (Cohort 3)	HIV negative subjects
Screening (Visit 1)	32,2	32,2	19,2
Day 1 (Baseline Visit)	167 – 169,7	167 – 169,7	124 – 126,7
Day 28 + Day 56 (Cohort 3)		167 – 169,7 + 38-40,7	
Day 28/84 (End of Rx Visit)	167 – 169,7	167 – 169,7	132,5 – 135,2
Day 35/91 (FU Visit)	33 – 35,7	33 – 35,7	20 – 22,7
Day 56/112 (EoS Visit)	83 – 85,7	83 – 85,7	48,5 – 51,2
TOTAL	482,2 – 493,0	687,2 – 703,4	345,2 – 354,0

Laboratory testing	Tube	Volume (ml)
Biochemistry	SST II advance (5ml)	5
Hematology	K3E 5,4mg (3ml)	3
INR&PT	9NC 0,129M (2,7ml)	2,7
Viral load (HIV)	K2E 18mg (EDTA) (10ml)	10
CD4/CD8 (HIV)	K3E 5,4mg (3ml)	3
HBV, HCV, HIV, syphilis screen (HIV and non-HIV, screening)	SST II advance (8,5ml)	8,5
HIV serology (non-HIV, screening day 28 and day 56)	SST II advance (8,5ml)	8,5
PK (per each PK timepoint)	CPT (8mL) + Li-Hep (4mL)	12
Blood for reservoir, immunology and Mol. Assays (HIV)	K2E 18mg (EDTA) (10ml) * 5	50
Blood for immunology and Mol. Assays (non-HIV)	K2E 18mg (EDTA) (10ml) * 2	20

5.6. Summary of rectal mucosal biopsies

Approximately 20 rectal mucosal punches (2.7 mm diameter) will be obtained during each flexible sigmoidoscopy procedure. Table 6 below summarizes the number and use of such rectal punches by study analysis.

Table 6: Number of rectal punches per study analysis

Study analysis	HIV-positive subjects	HIV-negative subjects
Explant HIV-1 infection	none	8
Flow cytometry	5	6
HIV-1 Reservoir	7	none
PK	4	4
Transcriptomics	1	1
Proteomics	1	1
TOTAL	18	20

The remaining biopsies, if any, will be cryopreserved at irsiCaixa.

